APPENDIX 2. DEFINITION OF WOMEN OF CHILDBEARING POTENTIAL AND CONTRACEPTION GUIDANCE

Definition of Women of Childbearing Potential

A woman is considered fertile after menarche and until becoming postmenopausal unless permanently sterile. If fertility is unclear (eg, amenorrhea in adolescents or athletes) and a menstrual cycle cannot be confirmed before administration of the first dose of study drug, additional evaluation should be considered.

A woman is not considered a WOCBP if any of the following apply:

- 1. Premenarchal
- 2. Premenopausal female with 1 of the following:
 - Documented hysterectomy
 - Documented bilateral salpingectomy
 - Documented bilateral oophorectomy

For individuals with permanent infertility due to an alternate medical cause other than the above (eg, Mullerian agenesis, androgen insensitivity), Investigator discretion should be applied to determining study eligibility.

Documentation can come from the subject's medical records, medical examination, or medical history interview.

- 3. Postmenopausal female
 - A postmenopausal state is defined as no menses for 12 months without an alternative medical cause.
 - A high follicle stimulating hormone (FSH) level in the postmenopausal range may be used to confirm a postmenopausal state in women not using hormonal contraception or hormone replacement therapy (HRT); however, in the absence of 12 months of amenorrhea, confirmation with >1 FSH measurement is required.
 - Females on HRT and whose menopausal status is in doubt will be required to use 1 of the nonestrogen hormonal highly effective contraception methods if they wish to continue their HRT during the study. Otherwise, they must discontinue HRT to allow confirmation of postmenopausal status before study enrollment.

Acceptable Contraception Methods

A highly effective form of contraception is defined as combined (estrogen and progestin containing) hormonal contraceptives (oral, intravaginal, or transdermal) known to be associated with inhibition of ovulation; progestin-only hormonal contraceptives (oral, injectable, or implantable) known to be associated with inhibition of ovulation; intrauterine device; intrauterine hormone releasing system; bilateral tube occlusion; or vasectomized partner. Hormonal contraception being used as a highly effective form of contraception must be accompanied by an acceptable barrier method.

An acceptable barrier method of contraception includes male or female condoms with or without spermicide, and cervical cap, diaphragm, or sponge with spermicide.

_	

AG348-C-018

RBC	Red blood cell		
RSD	Relative standard deviation		
SAE	Serious adverse event		
SAP	Statistical analysis plan		
SD	Standard deviation		
SOC	System organ class		
TDT	Transfusion-dependent thalassemia		
TEAE	Treatment-emergent adverse event		
T _{max}	Time of maximum observed concentration		

TRR	ransfusion reduction response	
ULN	Upper limit of normal	
WBC	White blood cell	
WHO	World Health Organization	

1. VERSION HISTORY

This statistical analysis plan (SAP) describes the analysis associated with protocol AG348-C-018 Amendment 2 (dated 28-September-2022).

2. INTRODUCTION

This SAP provides the detailed methodology for summary and statistical analyses of the data collected in Study AG348-C-018. This document may modify the plans outlined in the protocol; however, any major modifications of the primary endpoint definition or its analysis will also be reflected in a protocol amendment.

The primary clinical study report (CSR) will include all data for each subject up to the end of Double-blind (EODB) Period. The EODB period is defined as the end of the safety follow-up (for subjects who discontinue study treatment during the Double-blind Period) or before the start of study treatment in the Open-label Extension (OLE) Period (for subjects who continue onto the OLE Period after completing the Double-blind Period).

A CSR addendum will include data (associated with objectives that encompass OLE Period evaluations) through the End of Study (EOS). The EOS is defined as the time at which all subjects complete all study visits, are lost to follow-up, have withdrawn consent for further participation in the study, or when the Sponsor terminates the study. Study completion is the date of the last visit of the last subject in the study.

[figure not shown]
In the following sections, references to "EODB period date/EOS date" are meant to indicate that the EODB period subject-specific dates will be used for analyses to be reported in the primary CSR and the EOS date will be used for analyses to be reported in the addendum CSR.

3. OBJECTIVES AND ENDPOINTS

The study objectives and endpoints are provided in Table 2.

Table 2:Objectives and Endpoints

Primary Objective	Primary Endpoint
 To compare the effect of mitapivat versus placebo on transfusion burden in subjects with α- or β-transfusion-dependent thalassemia (TDT) 	• Transfusion reduction response (TRR), defined as a ≥50% reduction in transfused red blood cell (RBC) units with a reduction of ≥2 units of transfused RBCs in any consecutive 12-week period through Week 48 compared with baseline
Key Secondary Objective	Key Secondary Endpoints
• To compare the durability of the effect of mitapivat versus placebo on transfusion	• ≥33% reduction in transfused RBC units from Week 13 through Week 48 compared with baseline (TRR3)
burden	• ≥50% reduction in transfused RBC units in any consecutive 24-week period through Week 48 compared with baseline (TRR2)
	• ≥50% reduction in transfused RBC units from Week 13 through Week 48 compared with baseline (TRR4)
Secondary Objectives	Secondary Endpoints
• To evaluate the effect of mitapivat versus placebo on additional measures of	• Change from baseline in transfused RBC units from Week 13 through Week 48
transfusion burden	• Transfusion independence, defined as transfusion-free for ≥8 consecutive weeks through Week 48
• To evaluate the effect of mitapivat versus placebo on iron metabolism	• Change from baseline in iron, serum ferritin, total iron binding capacity, and transferrin saturation through Week 48
• To evaluate the safety of mitapivat	• Type, severity, and relationship of adverse events (AEs) and serious adverse events (SAEs)
• To evaluate the PK and PD effects of mitapivat	• Plasma or blood concentrations and PK parameters of mitapivat and PD parameters, including adenosine triphosphate (ATP) and 2,3-diphosphoglycerate (2,3-DPG)

[figure not shown]

4. STUDY DESIGN

This is a Phase 3, double-blind, randomized, placebo-controlled, multicenter study evaluating the efficacy and safety of mitapivat versus placebo in adult subjects with α - or β -TDT followed by an OLE Period. Approximately 240 subjects are planned to be randomized in this study. This multicenter study will be conducted internationally.

An overview of the study design is presented in Figure 1.

Figure 1: Study Design

Abbreviations: BID = twice daily; EOS = End of Study.

5. ANALYSIS DATA SETS

The following analysis data sets will be evaluated and used for presentation of the data:

Population	Description		
All Screened Subjects	All subjects who sign the informed consent form (ICF).		
Full Analysis Set (FAS)	All subjects who are randomized. Subjects will be classified according to the randomized treatment arm according to the intent-to-treat (ITT) principle. The FAS is the primary analysis set for the evaluation of efficacy endpoints, unless otherwise specified.		
Per-Protocol Set (PPS)	The PPS is a subset of the FAS. Subjects who meet any of the following criteria will be excluded from the PPS:		
	• Do not receive at least 1 dose of the randomized treatment		
	• Do not meet Inclusion Criterion #2 (ie, do not have documented thalassemia)		
	• Do not meet Inclusion Criterion #3 (ie, do not meet criteria for transfusion- dependent)		
	• Do not meet Inclusion Criterion #4 (ie, if taking hydroxyurea, the dose was not stable for ≥16 weeks before randomization)		
Safety Analysis Set	All subjects who receive at least 1 dose of study treatment. Subjects will be classified according to the treatment received. If a subject randomized to placebo receives at least 1 dose of mitapivat in the Double-blind Period, then the subject will be classified to the mitapivat arm.		
Open-label Extension (OLE) Analysis Set	All subjects who receive at least 1 dose of open-label mitapivat after the Double-blind Period		
Pharmacokinetic (PK) Analysis Set	A subset of the safety analysis set including all subjects with at least 1 mitapivat plasma concentration measurement \geq LLQ		
Pharmacodynamic (PD) Analysis Set	A subset of the safety analysis set including all subjects with at least 1 blood 2,3-DPG or ATP concentration measurement \geq LLQ		
PK/PD Analysis Set	A subset of the PK analysis set including all subjects in the PK and PD analysis sets, with at least 1 time-matched ATP or 2,3-DPG concentration to a mitapivat plasma concentration.		

Abbreviations: 2,3-DPG =2,3-diphosphoglycerate; ATP = adenosine triphosphate; ICF = informed consent form; ITT = intent-to-treat; LLQ = lower limit of quantification.

Table 3 summarizes the use of the analysis sets.

Endpoints	FAS	PPS	Safety Analysis Set	OLE Analysis Set	PK Analysis Set	PD Analysis Set	PK/PD Analysis Set
Demographic and other baseline characteristics	~			✓			
Disposition	~			✓			
Major protocol deviations	~			~			
Exposure and concomitant therapies			\checkmark	~			
Efficacy	~	 ✓ (primary and key secondary only*) 		~			
Safety			✓	~			
РК					~		
PD						\checkmark	
PK/PD							~

Table 3:Analysis Data Sets for Each Endpoint

* Key secondary endpoints are defined in Section 7.6.2.

Abbreviations: FAS = full analysis set; OLE = open-label extension; PD = pharmacodynamic; PK = pharmacokinetic; PPS = per-protocol set.

6. GENERAL STATISTICAL CONSIDERATIONS

6.1. Randomization, Blinding, and Unblinding

Eligible subjects will be randomized in a 2:1 ratio to mitapivat or matched placebo.

Randomization assignment will be implemented by an interactive voice/web response system (IXRS) and stratified by:

- Geographical region: North America and Europe; Asia-Pacific; rest of the world
- Thalassemia genotype:
 - subjects who do not have a β0 mutation at both alleles of the β-globin gene (non-[β0/β0]), including subjects with HbE/β-thalassemia and α-thalassemia/HbH disease;
 - subjects who have a $\beta 0$ mutation at both alleles of the β -globin gene ($\beta 0/\beta 0$).

This study includes a Double-blind Period followed by an OLE Period. Study subjects, Investigators, clinical study center personnel, pharmacists, and the Sponsor will be blinded to the subject's treatment assignment. After completing the Double-blind Period, subjects will be provided the opportunity to receive mitapivat in the OLE Period. At the last study visit of the Double-blind Period, subjects who continue in the OLE Period will be provided with active mitapivat; however, study subjects, Investigators, clinical study center personnel, and the Sponsor will continue to remain blinded to the randomized treatment assignment during the previous Double-blind Period until the study is unblinded for the analysis of the primary endpoint.

6.2. Sample Size Determination and Decision Rules

6.2.1. Sample Size Determination

The following statistical hypothesis will be tested to address the primary objective:

H₀₁: $p_{t1} - p_{c1} = 0$ vs H₁₁: $p_{t1} - p_{c1} \neq 0$

where p_{t_1} and p_{c_1} are the proportion of subjects achieving a TRR in the mitapivat arm and placebo arm, respectively.

Assuming a TRR response rate of 12.5% in the placebo arm, 240 subjects (160 subjects randomized to mitapivat and 80 subjects randomized to placebo) are needed to provide a 95% power to detect an increase in TRR response rate from 12.5% in the placebo arm to 33.7% in the mitapivat arm based on a 2-sided significance level of 0.05.

The conservative assumptions for the TRR rate were informed by the results of a Phase 3 clinical trial in patients with β -TDT where 12.5% was the upper bound of the 95% confidence interval (CI) for TRR rate in the placebo arm, and 33.7% was the lower bound of the 95% CI for the TRR rate for the active arm (Cappellini et al, 2020).

Additionally, the following statistical hypotheses will be tested to address the key secondary objectives:

[figure not shown]
H₀₂: $p_{t2} - p_{c2} = 0$ vs H₁₂: $p_{t2} - p_{c2} \neq 0$ H₀₃: $p_{t3} - p_{c3} = 0$ vs H₁₃: $p_{t3} - p_{c3} \neq 0$ H₀₄: $p_{t4} - p_{c4} = 0$ vs H₁₄: $p_{t4} - p_{c4} \neq 0$

where

- p_{t2} and p_{c2} are the proportion of subjects achieving a TRR2 in the mitapivat arm and placebo arm, respectively
- p_{t3} and p_{c3} are the proportion of subjects achieving a TRR3 in the mitapivat arm and placebo arm, respectively
- p_{t4} and p_{c4} are the proportion of subjects achieving a TRR4 in the mitapivat arm and placebo arm, respectively

Overall type I error will be maintained at or below a 2-sided significance level of 0.05 based on a graphical gatekeeping approach as illustrated in Figure 2.

Figure 2: Statistical Testing Strategy

The primary endpoint will be tested at a 2-sided α -level of 0.05. Then, the first 2 key secondary endpoints will be tested at an α -level of 0.032 and 0.018, respectively, if the null hypothesis for the primary endpoint is rejected. The last key secondary endpoint will be tested at an α -level of 0.018 (if only H₀₂ is rejected), 0.032 (if only H₀₃ is rejected), or 0.05 (if both H₀₂ and H₀₃ are rejected).

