6.2.2. Decision Rules

The study will have demonstrated that mitapivat is statistically significantly superior to placebo for TRR if the 2-sided p-value for the test of the difference in the TRR rate is ≤ 0.05 and the TRR rate is higher for the mitapivat arm than for the placebo arm.

To protect the integrity of the study and to preserve the type I error at or below 2-sided α =0.05, the testing strategy outlined in Section 6.2.1 will be followed and statistical significance will be achieved for mitapivat compared to placebo for each key secondary endpoint that can be tested per this strategy at the associated significance level.

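### As written, no alpha passes on after TRR4 is rejected, so TRR2 stays at 0.018 and TRR3 at 0.032; the scheme is valid but conservative, and passing H04's level back would add power within the same 0.05 bound

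*SAP*

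**What the plan says.** SAP 6.2.1 states the aim: "Overall type I error will be maintained at or below a 2-sided significance level of 0.05 based on a graphical gatekeeping approach". The primary endpoint is tested at 0.05. If it is rejected, the first two key secondary endpoints are tested at levels "of 0.032 and 0.018, respectively, if the null hypothesis for the primary endpoint is rejected". The last one, H04 (TRR4), is tested at 0.018 "if only H₀₂ is rejected), 0.032 (if only H₀₃ is rejected), or 0.05 (if both H₀₂ and H₀₃ are rejected". Protocol 10.1 gives the same rules. SAP 6.2.2 then ties the claims to these levels: significance is declared "for each key secondary endpoint that can be tested per this strategy at the associated significance level".

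The text does not name the endpoints beside 0.032 and 0.018. The H04 rule settles it: rejecting H02 releases 0.018 and rejecting H03 releases 0.032, so TRR2 holds 0.018 and TRR3 holds 0.032. The endpoint table in SAP Section 3 agrees, since it lists TRR3, then TRR2, then TRR4.

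**The concern.** H02 and H03 each have one fixed level, every possible level of H04 is listed, and no sentence says what happens to H04's level once H04 is rejected. Suppose TRR3 and TRR4 are both rejected and TRR2 gives p = 0.03. TRR2 is then declared non-significant, although 0.032 of alpha is no longer needed elsewhere. All three endpoints serve the one key secondary objective, durability of effect. At stake is a formal claim for the sustained 24-week response and, less often, for the 33% reduction over Weeks 13 to 48.

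**Working it through.** **1. The plan's own figures.** 0.032 + 0.018 = 0.05, as stated. The sample size passage says "240 subjects (160 subjects randomized to mitapivat and 80 subjects randomized to placebo) are needed to provide a 95% power" for a change "from 12.5% in the placebo arm to 33.7% in the mitapivat arm". With a pooled null variance: mean rate (2×0.337 + 0.125)/3 = 0.2663; null SE = √(0.2663×0.7337×(1/160 + 1/80)) = 0.0605; alternative SE = √(0.337×0.663/160 + 0.125×0.875/80) = 0.0526; power = Φ((0.212 − 1.96×0.0605)/0.0526) = 0.962. Exact Fisher power is 0.956. Both agree with the stated 95%, and the primary test is not affected by this point.

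**2. Which level belongs to which endpoint.** Suppose instead that H02 had 0.032 and H03 had 0.018, with the stated inheritance. With H03 rejected and H02 and H04 both null, the error could reach 0.032 + 0.032 = 0.064 (independent tests: 1 − 0.968² = 0.063). That would break the stated control, so TRR2 = 0.018 and TRR3 = 0.032 is the only coherent reading.

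**3. Closed-test levels.** The level used for each intersection of the three secondary hypotheses is:

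| Intersection | As written | H04's level passed back |
|---|---|---|
| H02, H03, H04 | 0.018 + 0.032 + 0 = 0.05 | same |
| H02, H03 | 0.018 + 0.032 = 0.05 | same |
| H02, H04 | 0.018 + 0.032 = 0.05 | same |
| H03, H04 | 0.032 + 0.018 = 0.05 | same |
| H04 | 0.05 | same |
| H02 | 0.018 | 0.05 |
| H03 | 0.032 | 0.05 |

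Only the last two rows fall short, by 0.032 and 0.018. Raising them to 0.05 changes nothing else. By closure, the 0.05 familywise bound still holds and everything rejected now is still rejected. None of this depends on assumed response rates.

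**4. Attained error.** Simulation used 2,000,000 draws of correlated test statistics, with correlation 0, 0.5 and 0.8. With only H02 null, error goes from 0.018 to 0.050. With only H03 null, it goes from 0.032 to 0.050. All other null configurations are unchanged and at most 0.05.

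**5. Power, by hand.** Assume independent tests, each with 80% power at 0.05. Power at 0.018 is Φ(2.802 − 2.366) = 0.669, and at 0.032 it is Φ(2.802 − 2.144) = 0.745. TRR2 gains when its p-value lies between 0.018 and 0.05 and TRR3 and TRR4 both pass at 0.032: (0.80 − 0.669)×0.745² = 0.073, so 0.669 becomes 0.742. TRR3 gains (0.80 − 0.745)×0.669² = 0.025, so 0.745 becomes 0.770. TRR4 gains nothing.

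**6. Power over a range.** All inputs here are assumptions. Simulated over the three correlations:

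| Assumed power at 0.05 (TRR2/TRR3/TRR4) | TRR2 gain, points | TRR3 gain, points |
|---|---|---|
| 80/80/80% | 5.7 to 7.3 | 1.2 to 2.5 |
| 60/90/80% | 10.4 to 13.2 | 0.1 to 1.1 |
| 80/60/60% | 1.4 to 3.7 | 2.0 to 2.2 |
| 50/50/50% | 2.9 to 4.9 | 0.8 to 1.2 |

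Binary endpoints simulated at 160 versus 80, with TRR4 responders nested within TRR3 and latent correlation 0.7 or 0.9:

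| Assumed placebo rates (TRR2/TRR3/TRR4) | Assumed mitapivat rates | TRR2 gain, points |
|---|---|---|
| 5/4/2% | 25/20/10% | about 0.5 |
| 8/6/3% | 25/20/12% | 2 to 4 |
| 5/5/2% | 20/20/12% | 3.8 to 5.4 |
| 6/6/3% | 16/18/12% | about 9 |

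In similar binary runs with TRR2 truly null, its false rejection rate went from about 1.6% to 3.4%.

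**The case against.** The strongest reply is that nothing is broken. The plan promises error at or below 0.05 and delivers it, and making the most demanding endpoint the last stop is a legitimate choice. That stands: a reader might infer a failure of type I error control, and the documents do not support it.

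Second, both documents refer to Figure 2 for the graph, and the figure is not in the text reviewed. A reader might infer that H04 certainly has no outgoing arrow. The documents do not support that much, because only the written rules are known to lack one. This also stands, and it makes part of the fix conditional.

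Third, one might infer that the change costs nothing in error. Only the 0.05 bound is unchanged. Attained error rises in the two configurations of step 4, and the added power comes from there.

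Fourth, one might expect a consistently large gain for TRR2. The documents give no secondary rates or correlations. The gain is close to nil when TRR2 is the stronger test and largest when it is the weaker. Where it arises, the trial already holds two durability claims over Weeks 13 to 48.

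An objection that edge weights would also have to be chosen does not stand. H04 can be tested only after H02 or H03 is rejected, so at most one of them is open, and any positive weights update to 1 on that one.

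**Conclusion.** On the written rules, the key secondary scheme is valid but conservative. It leaves 0.032 unused for TRR2, or 0.018 for TRR3, once the other two are rejected. Passing H04's level back never loses a rejection and sometimes adds one, within the same two-sided 0.05 familywise bound. That part is exact and rests only on the stated levels. The size is not exact: about 0 to 13 points of power for TRR2, about 0 to 2.5 for TRR3 and none for TRR4, all under assumed rates and correlations. This is an available improvement, not an error in the plan. Its one reservation is that the text cannot show what Figure 2 draws.

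**What to change.** Before unblinding, add to SAP 6.2.1 and Protocol 10.1 that, once H04 is rejected, its level passes to whichever of H02 or H03 is still open. H02 is then retested at 0.05 if H03 and H04 are rejected, and H03 at 0.05 if H02 and H04 are rejected. Draw both arrows in Figure 2 if they are not there. If they are, bring the text into line with the figure. In the same edit, name TRR3 beside 0.032 and TRR2 beside 0.018, which removes the ambiguity in step 2.

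The cost is a short protocol and SAP amendment, with the ethics committee approval that Protocol 11.1 requires for protocol changes. No subjects or data are added, and no hypothesis is tested at a lower level than now. The sponsor should accept knowingly that attained error may rise to 0.05 where the current text is stricter.

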6.2.2. Decision Rules

The study will have demonstrated that mitapivat is statistically significantly superior to placebo for TRR if the 2-sided p-value for the test of the difference in the TRR rate is ≤ 0.05 and the TRR rate is higher for the mitapivat arm than for the placebo arm.

To protect the integrity of the study and to preserve the type I error at or below 2-sided α =0.05, the testing strategy outlined in Section 6.2.1 will be followed and statistical significance will be achieved for mitapivat compared to placebo for each key secondary endpoint that can be tested per this strategy at the associated significance level.

6.3. Definitions

6.3.1. Study Drug and Study Treatment

In the Double-blind Period, both study drug and study treatment are defined as mitapivat or matched placebo.

In the OLE Period, both study drug and study treatment are defined as mitapivat.

6.3.2. Start and End Dates of Study Treatment

The start of study treatment is the earliest date/time of administration of a non-zero dose of the study drug.

The end of study treatment is the latest date/time of administration of a non-zero dose of the study drug on or before the EODB period date/ EOS date.

6.3.3. Study Day

The study day for assessments or events occurring on or after the start of study treatment (eg, AE onset, disease assessment) will be calculated as:

Study day=Date of the assessment or event-start of study treatment+1.

The study day for assessments or events occurring before the start of study treatment (eg, baseline characteristics, medical history) will be negative and calculated as:

Study day=Date of the assessment or event-start of study treatment.

There is no study day 0. The study day will be displayed in data listings.

6.3.4. Baseline

6.3.4.1. Double-blind Period

Throughout the SAP for analyses based on the Double-blind Period, 'reference date' will be used to refer to randomization date for subjects randomized and not dosed, or the start of study treatment for subjects randomized and dosed.

Efficacy Evaluations

The 24-week baseline transfusion burden is defined as the total number of RBC units transfused during the 24-week period (168 days) before the 'reference date'. Baseline transfusion burden will be standardized to match the postbaseline assessment duration specified for each endpoint associated with reduction of transfusion burden from baseline.

For iron metabolism (Section 7.6.3.2),

baseline is defined as the last assessment before Transfusion 0 (the last RBC transfusion that is administered before randomization) to minimize the impact of transfusion on these endpoints. Baseline will be derived based on central laboratory data; if no central laboratory data are available, then local laboratory data will be used to derive the baseline.

Demographic and Other Baseline Characteristics

For summaries of demographic and other baseline characteristics based on the FAS, baseline is defined as the last assessment before the 'reference date'.

Safety Evaluations

For clinical laboratory assessments the following applies:

• Before deriving the baseline:

- If there are multiple records with the same assessment day and time from the same laboratory, the average value will be used.
- If there are multiple records with the same assessment day and time from different laboratories, the value from the central laboratory will be used.
- The baseline will then be the last value before the start of study treatment.

For all other safety parameters, the last assessment before the start of study treatment will be used as the baseline.

PD Evaluations

The baseline is defined as the pre-dose whole blood concentration of 2,3-DPG and ATP on study day 1. If this concentration is <LLQ, baseline will be set to missing.

If, per protocol, an assessment is to be performed on study day 1, before the first dose of study treatment, and the assessment time, time of first dose of study treatment, or both are missing or not collected, it will be assumed that the assessment is performed before the first dose of study treatment. Unscheduled assessments will be used in the determination of baseline; however, an unscheduled assessment on study day 1 for which the time relative to start of study treatment cannot be determined, will be considered to have been obtained after administration of study treatment.

If no assessment meets the definition of baseline for an evaluation, the baseline will be set to missing.

